Annex 1.5. Assessment of success

Objectives	Questions	Is the question included in the assessment of success? (Yes/No)	Definition of desirably/correctly answered question	Assessment of success
Awareness of the RM tools	Q9. Did you or your hospital receive the VFEND (voriconazole) Healthcare Professional (HCP) Q&A Brochure?	Yes	Question completed desirably (Answer 1 is desirable)	An HCP is considered successful for awareness when he/she
	Q10. Did you or your hospital receive copies of the VFEND (voriconazole) Healthcare Professional (HCP) Checklist?	Yes	Question completed desirably (Answer 1 is desirable)	acknowledges receiving all RM tools Success for awareness: if
	Q11. Did you or your hospital receive copies of the VFEND (voriconazole) Patient Alert Card?	Yes	Question completed desirably (Answer 1 is desirable)	≥80% of HCPs are successful
	Q12. Did you or another staff member obtain the VFEND (voriconazole) RM tools by downloading them from a website?	No	Complementary question	
Reading and Utilizing the tools.	Q9.1 Did you read the VFEND (voriconazole) HCP Q&A Brochure?	Yes	Question completed desirably (Answers 1 & 2 are desirable)	An HCP is considered successful for utilization when
	Q10.1 Did you read the VFEND (voriconazole) Healthcare Professional (HCP) Checklist?	Yes	Question completed desirably (Answers 1 & 2 are desirable)	he/she reports reading all/some of all RM tools and
	Q11.1 Did you read the VFEND (voriconazole) Patient Alert Card?	Yes	Question completed desirably (Answers 1 & 2 are desirable)	always/sometim es using them Success for
	Q14. When treating patients with VFEND (voriconazole) in the past 12 months, how often did you use the VFEND HCP Checklist?	Yes	Question completed desirably (Answers 1 & 2 are desirable)	utilization: if ≥80% of HCPs are successful
	Q15. When treating patients with VFEND (voriconazole) in the past 12 months, how often did you use the HCP Q&A Brochure?	Yes	Question completed desirably (Answers 1 & 2 are desirable)	

	Q16. When treating patients with VFEND (voriconazole) in the past 12 months, how often did you distribute and fill in the Patient Alert Card? Q17. Did you find the VFEND (voriconazole) RM tools to be of use in your clinical practice? Please select only one rank for each RM tool (Q17.1, Q17.2 and Q17.3)	Yes No	Question completed desirably (Answers 1 & 2 are desirable) Complementary question	
Knowledge about the RM tools	Q7. According to the SPC/PI, the known risks for VFEND (voriconazole) are as follows: (Please select only one response for each of the risks listed in the table below.) Q8. Please select only one response for each statement about VFEND	Yes	Question completed correctly (6 points) Question completed correctly (5 points)	An HCP is considered successful for Knowledge when he/she provides at least 9 out of 11 (~80%) correct/desirable responses. Success for
Self-declared behavior/ Practice	(voriconazole) below: Q18. Which precautionary measures do you communicate to your patients for whom you	Yes	Question completed desirably (6 points)	Knowledge: if ≥80% of HCPs are successful An HCP is considered successful for awareness when he/she provides
	prescribe VFEND (voriconazole)? Please check all that apply. 18.a Do you, or another member of your healthcare team (e.g., nurse, pharmacist or other) perform each of these activities when initiating treatment with VFEND (voriconazole)? (Please check one response for each activity below).	Yes	Question completed desirably (6 points)	desirable responses to all sub-questions. Success for self-reported practices if ≥80% of HCPs are successful
	Q19. How frequently do you perform Liver Function Tests (specifically AST, ALT)?	Yes	Question completed desirably (Answer 1 is desirable)	

Q20. If there are no changes in Liver Function Tests (LFTs) after one month of initiation of VFEND (voriconazole), how often do you monitor liver function during VFEND treatment maintenance?	Yes	Question completed desirably (Answer 2 is desirable)	
Q21. How often do you perform a dermatologic evaluation when VFEND (voriconazole) is continuously used despite the occurrence of phototoxicity related lesions?	Yes	Question completed desirably (Answer 4 is desirable)	
Q22. For which of below condition(s) would you discontinue VFEND (voriconazole) in a patient? (Select the one best response).	Yes	Question completed desirably (Answer 4 is desirable)	

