8. RESEARCH OUESTION AND OBJECTIVES

The overall objective of the study is to evaluate the effectiveness of the aRMMs being implemented across Saudi Arabia to mitigate the risks of phototoxicity, SCC of the skin, and hepatic toxicity with the use of voriconazole.

Specifically, the objectives of this research are to:

1 Assess HCPs' awareness of the RM tools (ie, HCP Checklist, HCP Q&A Brochure and Patient Alert Card).

- 2 Assess HCPs' utilization of the RM tools (ie, HCP Checklist, HCP Q&A Brochure and Patient Alert Card).`
- 3 Assess HCPs' knowledge of the risks of phototoxicity, SCC of the skin, and hepatic toxicity with voriconazole.
- 4 Assess whether HCPs' self-reported practices with respect to minimising the risks of phototoxicity, SCC of the skin, and hepatic toxicity are in accordance with voriconazole SPC.¹

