9.1.1. Endpoints

- 1 The proportion of targeted HCPs who acknowledge receiving each of the RM tools.
- 2 The proportion of targeted HCPs who acknowledge reading and utilizing the tools.
- 3 The proportion of targeted HCPs who responds to correctly to questions about the risks of phototoxicity, SCC of the skin, and hepatic toxicity.
- 4 The proportion of targeted HCPs who provided desirable responses to the practicerelated questions and self-declared behavior with regard to strategies to mitigate the risks.

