9.4.1. Data Collection Process

Eligible HCPs (those HCPs to whom the RM tools were distributed by hand) will receive a letter by E-mail inviting them to participate in the survey. The invitation letter will include: an overview of the rationale for the survey, reminder about the educational materials, the secure URL to be copied and pasted into their browser, and a unique user identifier (ID). The survey data collection will be open until 10 completed surveys are received, up to 60-90 days. The survey start date begins within 12-18 months after initiation of distribution (05 February 2023) of the aRMMs tools in the Saudi Arabia.

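### Awareness items Q9–Q11 merge receipt by the HCP with receipt by the hospital, so the awareness score does not measure the HCP-level receipt that endpoint 1 defines

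*Protocol*

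**What the plan says.** Protocol section 9.1.1 defines endpoint 1 as "The proportion of targeted HCPs who acknowledge receiving each of the RM tools", and section 9.7 repeats it in similar terms. Under Annex 1.5 an HCP succeeds on awareness when he or she "acknowledges receiving all RM tools", and the programme succeeds on awareness when at least 80% of HCPs do.

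Three items feed that score, and Yes is the desirable answer to each:

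- Q9: "Did you or your hospital receive the VFEND (voriconazole) Healthcare Professional (HCP) Q&A Brochure"
- Q10: "Did you or your hospital receive copies of the VFEND (voriconazole) Healthcare Professional (HCP) Checklist"
- Q11: "Did you or your hospital receive copies of the VFEND (voriconazole) Patient Alert Card"

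The other two answers are No and not remembering receipt; both skip the reading question for that tool. The reading items Q9.1, Q10.1 and Q11.1 are addressed to the respondent alone. Section 9.4 lists them under awareness, while Annex 1.5 scores them under reading and utilization.

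Section 9.4.1 describes the invited HCPs as "those HCPs to whom the RM tools were distributed by hand". Section 9.5 plans for 10 completed surveys. Section 9.6 states that respondents will not be queried.

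**The concern.** The endpoint and the success rule are written for the individual HCP, but the items accept receipt by either of two parties. An HCP who was never given a tool, but knows that the hospital has it, can truthfully answer Yes to all three items and is then recorded as having received everything.

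The tools were handed out in person from a distribution list, so personal receipt is the step this endpoint should be able to check. With the merged Yes, a listed HCP whom the delivery missed looks the same as one whom it reached. The survey could then report success on awareness although fewer than 80% of respondents had received the tools themselves. The limitations section (9.9.2) discusses under-reporting of receipt through poor recall, but not this effect in the other direction.

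**Working it through.** **1. The plan's own figure.** 10 planned completers (section 9.5) and at least 80% successful (Annex 1.5): 0.80 × 10 = 8, so the rule is 8 of 10. Each respondent moves the result by 1/10 = 10 percentage points.

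**2. Direction and tipping point.** Among 10 completers, let *a* be the number who personally received all three tools and say so. Let *b* be the number who answer Yes to all three only because hospital receipt counts for at least one tool.

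- Score on personal receipt: a/10
- Score as written: (a + b)/10

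Since b cannot be negative, the wording can only raise the score. The verdict changes when a ≤ 7 and a + b ≥ 8. Two small cases:

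- a = 7, b = 1: 70% (fail) becomes 80% (success)
- a = 6, b = 2: 60% (fail) becomes 80% (success)

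**3. How much it could matter.** The documents give neither the personal receipt rate nor the rate of hospital-only answers, so both are assumptions here. Let *q* be the share of HCPs who personally received all three tools, and *h* the share of the rest who answer Yes to all three on the hospital's account. Then the chance of a full set of Yes answers is

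p = q + (1 − q) × h

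and, treating respondents as independent, the chance of meeting the rule is P(X ≥ 8) for X ~ Binomial(10, p).

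Worked case, q = 0.60 and h = 0.50: p = 0.60 + 0.40 × 0.50 = 0.80.

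- Personal receipt only (p = 0.60): 45 × 0.6⁸ × 0.4² + 10 × 0.6⁹ × 0.4 + 0.6¹⁰ = 0.17
- As written (p = 0.80): 45 × 0.8⁸ × 0.2² + 10 × 0.8⁹ × 0.2 + 0.8¹⁰ = 0.68

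The range, as the chance of reaching 8 of 10:

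| q (assumed) | personal only (also h = 0) | h = 0.25 | h = 0.50 | h = 0.75 |
|---|---|---|---|---|
| 0.40 | 0.01 | 0.10 | 0.38 | 0.82 |
| 0.60 | 0.17 | 0.38 | 0.68 | 0.93 |
| 0.80 | 0.68 | 0.82 | 0.93 | 0.99 |

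If nobody answers for the hospital (h = 0), the wording makes no difference.

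**4. Can the data be separated later?** No item records the route of receipt. Q12 (website download) is complementary and does not enter the score. The reading items show whether a tool was read, not how it was obtained. With no queries allowed, the split cannot be recovered after fielding.

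**The case against.** Several points on the other side stand.

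- The items ask about the HCP or the hospital. A reader might infer that the score captures delivery to the institution instead of to the HCP. The wording does not support that: it mixes the two.
- A reader might also infer that a hospital-only Yes comes from an unaware HCP. To give that answer the respondent must know that the tool arrived, and No and not remembering are offered separately. Such an HCP is arguably aware. The clear mismatch is with receiving, the term that endpoint 1 and the Annex 1.5 rule use.
- Invitees are described as having been handed the tools, which probably keeps hospital-only answers uncommon.
- Objective 2 requires personal reading and use of all three tools at the same 80% level. An HCP who never opened the hospital's copies therefore fails there.
- Poor recall, and leaving website downloads out of the score, push the figure down. Net overstatement is not shown, only overstatement relative to personal receipt as reported.
- The 80% threshold is not formally tested and the sponsor calls it subjective.
- Scoring personal receipt alone would fail on awareness an HCP who read and used the hospital's copies. That is a reason to report both figures, not to leave them merged.

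Two further inferences go too far. One is that every respondent from a hospital would answer Yes after a single delivery; that could happen, but nothing in the protocol establishes it. The other is that Q18a ("Do you, or another member of your healthcare team (e.g., nurse, pharmacist or other) perform each of these activities") shares the fault. Its team wording is explicit, it serves objective 4, and it includes distractor activities. Annex 1.5 requires desirable answers to all practice sub-questions, and the other practice items, Q18 and Q19–Q22, address the respondent. A team-level Yes cannot produce success by itself, and scoring Q18a by person is a design preference.

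**Conclusion.** The mismatch is real and can be verified within the protocol. The awareness score measures receipt by the HCP or the hospital, while endpoint 1 and the Annex 1.5 rule are stated for the HCP. Relative to personal receipt the effect runs upward only. Its size is unknown and may be small. The probabilities above illustrate assumed rates under independence and do not estimate what this survey would find. The point still deserves action because the rule is 8 of 10: one hospital-only answer suffices when seven HCPs personally received everything, two when six did, and the result could not be corrected afterwards.

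**What to change.** - In Q9, Q10 and Q11, replace Yes with two options: *Yes, I received it myself* and *Yes, my hospital received it but I did not personally*.
- Route both to the reading question, and treat both as Yes in the programming notes that open later items (Q14–Q17 and the Patient Alert Card row of Q18a), so that HCPs using hospital copies are still asked about them.
- In Annex 1.5, score endpoint 1 on personal receipt and report receipt by the HCP or the hospital as a separate row. If institutional receipt was what the sponsor meant, restate endpoint 1 (sections 9.1.1 and 9.7) and the Annex 1.5 rule accordingly.
- Align section 9.4 with Annex 1.5 on whether Q9.1, Q10.1 and Q11.1 belong to awareness or to utilization.

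The cost is one added response option in three questions, the matching routing notes and a scoring line, all cheap before the survey is programmed. The downside is a possibly lower awareness figure and slightly longer items.

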6. MILESTONES

Milestone	Planned date
Start of data collection	15 November 2024
End of data collection	15 February 2025
Registration in the HMA-EMA Catalogues of RWD Studies	10 November 2024
Final study report	30 June 2025

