9.1. Study design

This is a non-interventional, cross-sectional study to evaluate the effectiveness of RM tools for voriconazole. The study objectives will be accomplished by means of a cross-sectional, web-based survey of all HCPs who were targeted to receive the aRMMs and self-report as prescribers of voriconazole within 12 months preceding the survey in Saudi Arabia (Central, East and North regions). The study aims to obtain completed surveys from 10 HCPs. Data will be collected until 10 completed surveys are obtained or up to a data collection period of 60 to 90 days as a maximum. The data from the HCPs will be collected using a structured self-administered questionnaire to gather evaluation metrics related to the utilization and understanding of RM tool content and messages. In addition, the survey will assess behaviors, including a set of hypothetical scenarios for HCPs. The survey is not intended to be a mechanism for collecting adverse events (AEs), nor is it intended to result in minimizing the numbers of AEs reported. HCPs will be invited by e-mail to participate in the survey and asked to complete the online questionnaire.

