9.2. Setting

The target population will include all HCPs who were targeted to receive Vfend® aRMM materials within 12 months preceding the survey.

At the time of protocol writing, approximately to HCPs were prescribing/dispensing voriconazole in Saudi Arabia and around of these targeted to receive the RM tools in-person, per Pfizer Inc.'s Distribution List. Given this relatively small pool of HCPs, an empirical sample size of 10 HCPs is proposed.

HCPs recruitment and survey will be conducted by the following process:

- HCPs will be invited to participate in the survey by email and/or phone. An email
 invitation will include a web link directing to a webtool named 'Decipher', where the
 survey questionnaire will be available. In the invitation, the survey background and
 objectives, the contact information for questions will be explained to the HCPs.
 Instructions detailing the survey requirements will be displayed at the start of the
 survey.
- If the HCPs agree to participate in the survey, they can access the survey and the instructions for the web questionnaire by clicking on the email link.
- If the questionnaire is not completed in the first attempt, HCPs will receive a reminder email and/or phone (first reminder) 1 week after the initial invitation.
- If the web questionnare remains incomplete, a second reminder will be sent about 2 weeks after the initial invitation.
- If the questionnaire still remains incomplete, a third (and final) reminder will be sent 3 weeks after the initial invitation.

An HCP will be considered unreachable if he/she has been contacted up to 3 times without an answer. For each recruited HCP, the number of times the HCP is contacted, as well as the date and time when he/she completes the web questionnaire, will be recorded. HCP recruitment will be competitive.

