9.2.1. Inclusion criteria

Participants/ HCPs must meet all of the following criteria to be eligible for inclusion in the survey:

- 1. Willing/consent to participate in this self-administered survey.
- 2. Involved in the treatment of at least 1 patient with voriconazole within the last 12 months.

Evidence of an electronically signed and dated informed consent document indicating that the participant/ HCP has been informed of all pertinent aspects of the study.

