9.5. Study Size

At the time of protocol writing, a total of HCPs (distribution list shared with Saudi Food and Drug Authority [SFDA]) are expected to initiate or manage patients on Vfend®. All HCPs who were targeted to receive the RM tools (per Pfizer Inc.'s Distribution List.) within the 12 months preceding the initiation of the survey will be invited to participate in the survey. Given this relatively small pool of HCPs, an empirical sample size of 10 HCPs is proposed. Data will be collected until 10 completed surveys are obtained or up to a data collection period of 60 to 90 days as a maximum. It is important to note that the final survey sample size will depend on HCPs' willingness to participate in the survey.

An a priori threshold of 80% correct responses per risk question will be used to define the success of the program. However, this criterion will not be used for formal statistical testing. The selection of this threshold for success was regarded as being subjective and not based on prior knowledge, experience, or established scientific criteria.

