Annex 1.1. Abstract

Title

Evaluation of the effectiveness of additional risk minimisation measures (aRMMs) that aim to reduce the risks of phototoxicity, squamous cell carcinoma (SCC) of the skin and hepatic toxicity in patients receiving voriconazole in the Saudi Arabia.

Protocol version and date

Version 1.0 16 August 2024

Name and affiliation of main author

Rationale and Background

Pfizer Saudi Limited will conduct a non-interventional, cross-sectional survey of healthcare professionals (HCPs) to evaluate the effectiveness of the aRMMs being implemented across Saudi Arabia to mitigate the risks of phototoxicity, SCC of the skin and hepatic toxicity in patients prescribed voriconazole (Vfend®), a broad spectrum triazole antifungal agent used to treat or prevent a range of serious fungal infections in both inpatient and outpatient settings.

To ensure that the risks are adequately managed, aRMMs in Saudi Arabia have been implemented since February 2023. The aRMM material distribution has been started on 05-February-2023 and continued until 05-February-2024 to the relevant HCPs who may initiate or manage patients on Vfend[®]. These include an updated voriconazole Summary of Product Characteristics (SPC)¹ (routine) and a new comprehensive education programme at the point of patient care that will educate/remind HCPs about the risks of phototoxicity, SCC of the skin and hepatic toxicity and how to manage them. The details of the Risk Minimisation (RM) tools for the educational programme and how these tools will be implemented across Saudi Arabia are described in the Risk Management Plan (RMP). The RM tools are the HCP Checklist, HCP Question & Answer (Q&A) Brochure and Patient Alert Card. HCPs who the materials are targeting will be invited to participate in the survey. The start of the data collection is intended to be within 18-24 months period from the launch of Vfend[®] in Saudi Arabia to allow physicians time for familiarity and use of the materials before evaluating the effectiveness of Vfend[®] aRMM.

Research Question and Objectives

The overall objective is to evaluate the effectiveness of the aRMMs to mitigate the risks of phototoxicity, SCC of the skin and hepatic toxicity in patients using voriconazole. The

Redacted

evaluation is being conducted in Saudi Arabia where RM tools are being implemented. Specifically, the objectives of the study are to:

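### The tool-use questions (Q14-Q16) look back a full 12 months without starting the count when the HCP had the tool, so use can be under-reported for recently supplied HCPs

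*Protocol*

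**What the plan says.** Annex 1.5 lists three utilisation items with the same look-back. Q14 reads "When treating patients with VFEND (voriconazole) in the past 12 months, how often did you use the VFEND HCP Checklist"; Q15 and Q16 repeat the period for the brochure and the alert card. In Annex 1.2 the only answers are *Always*, *Sometimes* and *Never*. Each item is shown if the HCP reports receiving that tool (Q9, Q10 or Q11) or a website download (Q12). Annex 1.5 counts the first two answers as desirable, and an HCP succeeds on utilisation only if all three tools were read and used. The objective is met if at least 80% of HCPs succeed.

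On the population, Section 9.2 states: "The target population will include all HCPs who were targeted to receive Vfend® aRMM materials within 12 months preceding the survey". Section 9.5 says that the HCPs targeted "within the 12 months preceding the initiation of the survey will be invited to participate in the survey". Section 9.1 is looser and describes HCPs "targeted to receive the aRMMs and self-report as prescribers of voriconazole within 12 months preceding the survey", where the 12 months can be read as belonging to prescribing. Section 9.4.1 calls eligible those who were handed the tools and gives no time limit. Section 9.2.1 requires only that the HCP be "Involved in the treatment of at least 1 patient with voriconazole within the last 12 months".

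On dates, Annex 1.1 says "The aRMM material distribution has been started on 05-February-2023 and continued until 05-February-2024". Section 6 sets data collection from "15 November 2024" to "15 February 2025".

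**The concern.** A tool can be used only after it is in hand. If receipt falls inside the look-back, patients treated earlier in the window count as occasions of non-use although use was impossible. An HCP who used the checklist for every patient since receipt, but treated one before it, cannot truthfully answer *Always*. An HCP whose only voriconazole treatment in the window came before receipt still meets the inclusion criterion, passes the receipt filter, and has only *Never* to choose.

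The error runs in one direction and would read as poor uptake. It cannot be repaired afterwards: no item asks when the tool was received, Section 9.9.2 makes every question compulsory, and Section 9.6 rules out queries to respondents. Utilisation is one of the four objectives, and Section 9.7 promises frequency distributions with 95% confidence intervals for the questions that address them.

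**Working it through.** The protocol states no figure for this overlap, so there is none to reproduce. The check is calendar arithmetic.

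**Inputs.** Distribution ran 05 February 2023 to 05 February 2024, 365 days (Annex 1.1). Data collection runs 15 November 2024 to 15 February 2025 (Section 6). The look-back is 12 months (Q14-Q16).

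**Largest part of the window before receipt** = max(0, 05 February 2024 minus [response date minus 12 months]) / window length. An HCP supplied on the last distribution day reaches it.

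| Response date | Window starts | Most days before receipt | Share |
|---|---|---|---|
| 15 Nov 2024 | 15 Nov 2023 | 82 | 82/366 = 22.4% |
| 06 Dec 2024 | 06 Dec 2023 | 61 | 61/366 = 16.7% |
| 31 Dec 2024 | 31 Dec 2023 | 36 | 36/366 = 9.8% |
| 14 Jan 2025 | 14 Jan 2024 | 22 | 22/366 = 6.0% |
| 05 Feb 2025 or later | 05 Feb 2024 or later | 0 | 0 |

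The second row is three weeks after the first possible invitation, when Section 9.2 sends the last reminder.

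**Who is affected.** On the literal wording of Sections 9.2 and 9.5, HCPs surveyed on the first day were supplied between 15 November 2023 and 05 February 2024. If receipt is spread evenly over those 82 days, the mean share before receipt is 41/366 = 11.2%. If instead all HCPs supplied since 05 February 2023 are invited, 82/365 = 22.5% of distribution days fall in the window, and the mean over everyone is about 0.225 × 11.2% = 2.5%.

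**Effect on answers at the first survey day**, for an HCP supplied inside the window. Assume treatment dates spread evenly, each patient a single point in time, and f = 82/366 = 0.224.
- No patient after receipt: f/2 = 11.2% with one patient (f = 22.4% if supplied on the last day); f²/3 = 1.7% with two.
- At least one of five patients before receipt, so *Always* is untrue: 1 − [1 − (1 − f)⁶]/(6f) = 42%; 1 − (1 − f)⁵ = 72% if supplied on the last day.

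**Effect on the criterion.** *Always* and *Sometimes* score alike, so only a forced *Never* counts. One such answer from an HCP who would otherwise have succeeded turns 8/10 (80%) into 7/10 (70%).

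**The case against.** The strongest reply is that the success criterion hardly moves. Shifting an answer from *Always* to *Sometimes* costs nothing in Annex 1.5, and a forced *Never* needs every voriconazole patient in the window to precede receipt. The single-point assumption probably overstates even that. The checklist image in Annex 1.2 asks for completion at each visit, and treatment can be long, so a patient started before receipt may still give occasion for use. Section 7 speaks of new patients instead, so the instruction is mixed, but the point is fair. No document says that HCPs typically have one patient; the lowest band in Q13 is 1 to 5.

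A reader might also infer that the whole target population is affected, or that the overlap could reach half the window or more. The documents do not support either. The first rests on the wording of Sections 9.2 and 9.5, which Sections 9.1 and 9.4.1 do not clearly share. On the milestone dates, everyone supplied in the distribution period had the tools for at least 284 days before the first possible response. The second would follow from the start window of 12 to 18 months in Section 9.4.1, but that window closed on 05 August 2024, before the protocol's own date of 16 August 2024.

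Finally, Section 9.9.2 relies on 12 months of recent use to limit recall bias. Asking simply about all time since receipt would stretch recall to about 21 months for an HCP supplied in February 2023. That objection stands and shapes the fix.

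None of this removes the gap in the questions: they are not tied to possession of the tool, and an HCP without opportunity has no truthful answer except one scored as failure.

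**Conclusion.** The point holds as a limited questionnaire defect. For HCPs supplied after mid-November 2023 who answer early, up to 22.4% of the look-back precedes receipt; the share declines through the collection period and is 0 from 05 February 2025. The main consequence is a downward bias in the reported *Always*/*Sometimes* distribution. A reader might infer that the 80% utilisation result is itself seriously at risk; the scoring does not support that, because it changes only through uncommon forced *Never* answers, each worth 10 points with 10 HCPs.

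The sizes assume that receipt fell within the stated distribution dates and that the Section 6 milestones hold. Website downloads are undated and could lengthen the period without the tool for individual HCPs. The chances of particular answers rest on the even-spread and single-point assumptions and are best taken as upper guides.

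**What to change.** Before programming:

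1. Reword Q14-Q16 along these lines: *In the past 12 months, since you received or obtained the tool, when treating patients with VFEND, how often did you …*. This keeps the 12-month recall cap.
2. Add the answer *I have not treated a patient with VFEND since then*.
3. In Annex 1.5, leave HCPs who choose that answer out of the utilisation denominator and report their number. Say how an HCP is handled who chooses it for one tool only.
4. Reconcile the 12-month targeting window in Sections 9.2 and 9.5 with Sections 9.1 and 9.4.1 and the distribution dates in Annex 1.1, so that it is clear who is invited.

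The cost is the wording of three questions, one answer option and a line or two in Annex 1.5. The downside is a possibly slightly smaller denominator. With one HCP left out of 10, the criterion needs 8 of 9, since 7/9 = 77.8%; that is the same 8 successes as 8 of 10. So one exclusion corrects the reported percentage without changing pass or fail. With two left out, 7 of 8 (87.5%) meets the criterion, where 7 of 10 would not.
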